2.2.2 Secondary Endpoints

1. The secondary safety endpoints are the following:
 - a. The percentage of subjects experiencing the following events: SAEs, temporally-related AEs, increased risk scores for DVT or PE, TEEs, inhibitory anti-C1-INH antibodies, or clinically significant abnormalities in laboratory assessments (ie, lab abnormalities reported as AEs).
 - b. The percentage of administrations of CSL830 resulting in solicited local AEs (discomfort [eg, pain, burning], swelling, bruising, or itching at the CSL830 injection site).
 - c. The percentage of subjects who have at least 1 solicited local AE (discomfort [eg, pain, burning], swelling, bruising, or itching at the CSL830 injection site).
 - d. The percentage of subjects who become seropositive for HIV-1/-2, HBV, or HCV.

The secondary safety endpoints will be assessed for Treatment Period 1, Treatment Period 2 and Treatment Periods 1 and 2 (together). The secondary safety endpoints will also be assessed for the Extension Period (only) and for the treatment periods overall for subjects who are included in the Extension Period.

2. Efficacy endpoints considered as secondary include the following:
 - a. The percentage of subjects who experience a time-normalized HAE attack frequency of < 1 HAE attack per 4-week period.
 - b. The percentage of subjects who are responders. “Response” is defined as a $\geq 50\%$ relative reduction in the time-normalized number of HAE attacks during treatment with CSL830, compared with the time-normalized number of attacks that is used to qualify the subject for participation in this study (see [Section 4.1.2](#) [inclusion criterion 5]).

The secondary efficacy endpoints will be assessed for Treatment Period 1, and Treatment Periods 1 and 2 (together). The secondary efficacy endpoints will also be assessed for the Extension Period (only) and for the treatment periods overall for subjects who are included in the Extension Period.

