11.3.3.2 Secondary Safety Analyses

Adverse event data will be presented in individual listings and summary tables.

The number and percentage of subjects experiencing SAEs, temporally-related AEs, increased risk scores for DVT or PE, thromboembolic events, inhibitory anti-C1-INH antibodies, or clinically significant abnormalities in laboratory assessments during treatment will be summarized as defined above in [Section 11.3.3](#) and overall. The number and percentage of subjects who become seropositive for HIV-1, HIV-2, HBV, or HCV will be summarized as defined above in [Section 11.3.3](#) and overall. The number and percentage of subjects experiencing solicited local AEs, the number of solicited local AEs, and the number of solicited local AEs per administration will be summarized as defined above in [Section 11.3.3](#) and overall. The number and percentage of administrations of CSL830 resulting in solicited local AEs will be summarized as defined above in [Section 11.3.3](#) and overall. An overall summary of AEs will be given.

Temporally-related AEs will be defined as AEs which began within 24 hours of administration of CSL830. Note that temporally-related AEs are referenced as “suspected ADRs” in study CSL830_3001. Temporally-related AEs occurring during treatment will be summarized as defined above in [Section 11.3.3](#) and overall in the current study (CSL830_3002).

Summaries will include the number and percentage of subjects, the number of AEs, and the number of AEs per administration and per week (where applicable) and will also be summarized as defined above in [Section 11.3.3](#) and at study visits. Summaries by SOC and PT will also be presented.

Adverse events will also be described by intensity, relationship to CSL830, duration, and seriousness.

The safety analyses will be conducted for Treatment Period 1 (only), Treatment Period 2 (only), and for Treatment Period 1 and 2 (together). For the subjects who are in the Extension Period, the safety analyses will be conducted for the Extension Period and for the treatment periods overall.

11.3.4

CCI [Redacted]

CCI [Redacted]

CCI [Redacted]

[Redacted]

[Redacted]

CCI [Redacted]

[Redacted]

[Redacted]

[Redacted]

[Redacted]

CCI [Redacted]

[Redacted]

[Redacted]

[Redacted]

CCI [Redacted]
CCI [Redacted]

[Redacted]
[Redacted]

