2.2 Secondary endpoints

2.2.1 Secondary safety endpoints

The secondary safety endpoints are the following:

- AEs,
- Solicited AEs,
- Unsolicited AEs,
- SAEs,
- Temporally-related AEs (AEs which start within 24 hours of administration of the investigational product),
- Suspected adverse drug reactions (ADRs) (AEs which start within 24 hours of administration of the investigational product or which are related to investigational product administration including AEs with missing causality rating),
- The CSL830 injections followed by at least one solicited AE,
- Subjects reporting CSL830 injections followed by at least one solicited AE,
- Risk scores for deep vein thrombosis (DVT) or pulmonary embolism (PE),
- TEEs,
- Hypersensitivity,
- Anaphylaxis,
- Clinical laboratory assessments:
 - Hematology.
 - Biochemistry.
 - Urinalysis.
 - Coagulation profile.
 - Anti-C1-INH antibodies.
 - Viral serology.
- Vital signs including body weight,
- Physical examination.

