4.7.2.3 Analysis of Laboratory Findings

Normal ranges will be provided for laboratory tests. Values outside the normal range will be judged as clinically significant or non-clinically significant by the investigator. All abnormal laboratory data considered as clinically significant will be presented as AE.

All continuous laboratory parameters will be plotted against their scheduled assessments visits.

Analyses of haematology, biochemistry, and coagulation parameters will consist of the following:

- Descriptive statistics for baseline and each treatment visit, including changes from baseline to each treatment visit
- Mean values and the SD of the continuous laboratory parameters at each scheduled visit will be plotted against scheduled visits.

Baseline will be the assessment before the first injection (Week 1 Day 1) for all “CSL830-Naïve” and “CSL830-Interrupted” Subjects and “CSL830-Continuation” Subjects who did not complete the assessments at the CSL830_3001 End of Study Visit. For “CSL830-Continuation” Subjects who complete the assessments at the CSL830_3001 End of Study Visit, these assessments will be the baseline. If the baseline value for a subject is missing, no change from baseline will be calculated for the subject.

The number and percentage of subjects without anti-C1-INH antibodies and with anti-C1-INH antibodies (inhibitory, non-inhibitory and inhibitory and non-inhibitory combined) during the study will be summarized overall and for each study visit

Urinalysis, viral serology and pregnancy testing results will be listed only.

Notes:

- All results outside predefined normal ranges will be flagged as high or low in the data listings.
- Clinically significant laboratory values will be flagged in the listings.
- Unscheduled results will be listed only and not included in summary tables.

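### The protocol requires a summary of HIV, HBV and HCV seroconversion as a secondary safety endpoint; the SAP plans only a listing, and its readable list of changes does not declare this

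*SAP*

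**What the plan says.** **Protocol.** Section 2.2.2, item 1d, defines a secondary safety endpoint: "The percentage of subjects who become seropositive for HIV-1/-2, HBV, or HCV". The same section has the secondary safety endpoints assessed for Treatment Period 1, Treatment Period 2, the two together, and the Extension Period. Section 11.3.3.2 gives the analysis: "The number and percentage of subjects who become seropositive for HIV-1, HIV-2, HBV, or HCV will be summarized", by the groups of Section 11.3.3 and overall.

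**SAP.** Section 2.2.1 keeps "Viral serology" as an entry under the clinical laboratory assessments that count as secondary safety endpoints, but without a percentage and without the idea of becoming positive. Section 4.7.2.2 confirms that HIV types 1 and 2, HBV and HCV are collected. Section 4.7.2.3 then states: "Urinalysis, viral serology and pregnancy testing results will be listed only". Section 4.14, which sets out the changes from the protocol, does not mention viral serology in its readable text.

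**The concern.** A secondary endpoint defined as a percentage has no planned percentage. Virus transmission is the first risk discussed in Protocol Section 1.4, because the product is derived from human plasma, and serology is drawn repeatedly to address it. If the SAP is followed as written, the study report will contain individual results but no statement of how many subjects could have converted and how many did.

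Two choices are also left open: what counts as a conversion, and who belongs in the denominator. If someone later builds the figure from the listing, both will be settled with the results in view. The study is open-label and the endpoint is descriptive, so the risk of bias is modest, but a pre-specified endpoint should not depend on such choices.

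**Working it through.** **1. The two documents side by side**

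| Item | Protocol | SAP |
|---|---|---|
| Endpoint | Percentage who seroconvert (2.2.2, 1d) | Viral serology, no measure given (2.2.1) |
| Analysis | Count and percentage in a summary (11.3.3.2) | Listing only (4.7.2.3) |
| Definition of conversion | Not spelled out | None |
| Denominator | Subjects; at-risk set not spelled out | None |
| Change declared | n/a | Not in the readable text of 4.14 |

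**2. Is the listing-only rule a real restriction?** Yes. SAP Section 4.1 already puts all data into by-subject listings, so restricting serology to a listing removes any analysis beyond the default.

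**3. Does it look deliberate?** The documents do not settle this. Two features point to an oversight. In the same SAP section the antibody endpoint does get a summary: "The number and percentage of subjects without anti-C1-INH antibodies and with anti-C1-INH antibodies". And Section 4.14 does declare another move to listing only, for adverse events during screening, so such changes were being recorded.

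**4. Is the endpoint covered elsewhere in the SAP?** Section 4.7.2.3 also says "All abnormal laboratory data considered as clinically significant will be presented as AE". Section 4.7.2.1 tabulates adverse events by system organ class and preferred term, with percentages based on the Safety Population. A conversion could therefore appear there, but only if the investigator judges it clinically significant, and over a denominator that is not limited to subjects negative at baseline.

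**5. Are the data available?** Yes. The protocol's laboratory schedules draw serology at Day 1 (or use the preceding study's final visit for Continuation subjects), Week 25 and Week 53. Sections 8.4.6.12 and 8.4.6.22 add Extension Weeks 48 and 88.

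**6. The plan's own figure.** SAP Section 3.8 says that 100 subjects allow at least one event to be seen, for an event probability of 3%, at 95% confidence. Check: 1 − 0.97^100 = 0.952. It reproduces, and nothing in this point disputes it.

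**7. Illustration of what an interval would add.** With no conversions among N subjects at risk, the exact two-sided 95% upper limit is 1 − 0.025^(1/N).

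- N = 100 (planned completers): 1 − 0.025^(1/100) = 3.6%. The one-sided limit, 1 − 0.05^(1/100) = 3.0%, matches the 3% in SAP Section 3.8.
- N = 55 (about 110 randomized, divided by 2): 1 − 0.025^(1/55) = 6.5%.
- N = 50 (approximate Extension enrollment): 1 − 0.025^(1/50) = 7.1%.

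These denominators are assumptions: every subject is taken to be negative at baseline with at least one later result. The 55 further assumes an even split and ignores dose increases.

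**The case against.** Several objections have force.

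- **The information is not lost.** A reader might infer that the endpoint can never be estimated, or that a listing conceals who was at risk. The documents do not support that. By-subject listings sorted by treatment, subject and time point show baseline and later results, so the at-risk subjects and the conversions can be counted by hand. What is missing is the planned summary and its rules.
- **The adverse event tables are a second route.** This stands as a partial safeguard for clinically significant conversions. It does not deliver item 1d, for the reasons in step 4.
- **No interval was planned.** Protocol Section 11.3 and SAP Section 4.1 describe categorical values by counts and percentages. With no conversions, the summary the protocol requires would show 0 (0.0%) and no upper limit. The figures in step 7 therefore show the value of an addition; they do not measure the departure from the protocol.
- **Not everything is visible.** Parts of SAP Section 4.14 are blacked out, and the table shells are a separate document (SAP Section 5.3). A serology table in the shells cannot be ruled out, but it would conflict with Section 4.7.2.3, which would still need correcting.
- **Dose attribution is awkward.** With few draws, a conversion in a subject whose dose rose between samples cannot be assigned to one dose with certainty. This is a reason to state a rule, not to omit the table.

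**Conclusion.** The inconsistency holds. The protocol requires a count and percentage of seroconversions, the SAP plans a listing, and the readable list of changes is silent. The consequence is an unsummarized secondary safety endpoint whose definition and denominator are unset before the data are seen.

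The severity is minor to moderate: the endpoint is descriptive, the data are collected, the count is recoverable, and the primary endpoints and sample size are untouched. It would go too far to conclude that viral safety goes unexamined or that the risk cannot be bounded from the reported data. The conclusion rests on the readable SAP text. The upper limits of 3.6%, 6.5% and 7.1% rest on assumed denominators and on there being no conversions.

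**What to change.** Remove viral serology from the listing-only sentence in SAP Section 4.7.2.3 and add one table:

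- **Measure:** n/N (%) of subjects negative at baseline who are positive at a later visit, for each virus and for any virus. N is the baseline-negative subjects with at least one later result.
- **Groups:** ≥ 40 IU/kg, and by dose with a stated attribution rule. One option is the dose at the first positive sample, flagging subjects whose dose rose since their last negative sample. This fits the by-actual-treatment approach that SAP Section 4.14 declares for secondary safety endpoints.
- **Periods:** Treatment Period 1, Treatment Period 2, both together, and the Extension Period, as in Protocol Section 2.2.2. SAP Sections 4.1 and 4.14 otherwise present the periods jointly, so the period split must be stated for this table. State also that the Week 25 sample counts for Treatment Period 1, because SAP Section 3.1.3 places that visit outside the period.
- **Optional:** an exact 95% confidence interval for each percentage.

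If the sponsor prefers a listing, the smaller remedy is to declare and justify the change in Section 4.14. The table is the better choice. It costs one extra output from data already collected, with no change to study conduct or sample size.

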4.7.3 Vital Signs and Body Weight

Results of vital signs and body weight will be summarized by visit. Descriptive statistics for baseline and each treatment visit will be displayed. Descriptive subgroup analysis will be done for subjects who use any oral Prophylaxis for Treatment of HAE during the study.

Baseline will be Week 1 Day 1 for all “CSL830-Naïve” and “CSL830-Interrupted” Subjects and “CSL830-Continuation” Subjects who did not complete the assessments at the CSL830_3001 End of Study Visit. For “CSL830-Continuation” Subjects who complete the assessments at the CSL830_3001 End of Study Visit, these assessments will be the baseline. All vital signs and body weight data will be listed and abnormal results will be flagged.

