3.5 Planned Number of Subjects

The study plans to enroll subjects who complete participation in CSL830_3001. Additional subjects who have not participated in study CSL830_3001 will be enrolled so that the total number of subjects randomized is approximately 110.

Assuming that up to 10% of subjects withdraw before the completion of the study, 100 subjects are planned to complete the study.

Subjects from the United States who have completed Treatment Period 1 and Treatment Period 2 according to the study protocol are eligible to enroll in the Extension Period. Approximately 50 of these subjects are anticipated to enroll in the Extension Period.

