4.1 Planned Analyses

The data from Treatment Period 1, Treatment Period 2, and Extension Period will be analyzed and presented jointly, unless specified otherwise.

For subjects who are not participating in the Extension Period, the End of Study Visit will be at Week 53. For subjects who are participating in the Extension Period, the End of Study Visit will be at Week 88.

All summary tables will be presented by treatment groups 40 IU/kg CSL830, 60 IU/kg CSL830, and ≥ 40 IU/kg CSL830 unless specified differently. Events occurring under 80 IU/kg will be summarized in the ≥ 40 IU/kg CSL830 treatment group and otherwise listed only.

Subject disposition will be summarized for all subjects who provide informed consent/assent (as appropriate). Demographic and subject characteristics will be summarized using the ITT and Safety Populations.

All safety data will be summarized using the Safety Population. The analysis of the safety endpoints will be by actual CSL830 treatment (40 IU/kg CSL830, 60 IU/kg CSL830, or ≥ 40 IU/kg CSL830) the subject was taking when the event occurred, unless specified otherwise. In the analysis as treated, a subject contributes events or assessments to each treatment received, e.g. a subject randomized and treated with 40 IU/kg and up-titrated and treated with 60 IU/kg will be displayed in both treatments as well as displayed once in the ≥ 40 IU/kg treatment.

The efficacy endpoints considered as secondary will be summarized using the ITT and PP Populations. CCI

CCI

CCI

Continuous variables will be described by using the mean value with the respective 95% confidence intervals (CI) [only for efficacy variables]; standard deviation; range; 25th, 50th (median), and 75th percentiles; and counts of missing and non-missing values. The geometric coefficient of variation will be expressed as a percentage and the geometric mean and respective 90% CI will be calculated for CCI. The 90% CI for the geometric mean will be calculated by log transforming the data, calculating the lower and upper limits of the 90% CI of the mean of the log-transformed data and, subsequent back transforming the lower and upper limits. Categorical values will be described using counts and percentages. Time variables will be described by median, minimum and maximum and if applicable in addition by mean, standard deviation, 25th and 75th percentiles and graphically represented by Kaplan-Meier curves with the respective 95% CI.

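### SAP 4.7.3 tabulates vital signs and body weight as raw values by visit with no within-subject change, so the Extension columns can shift through who remains; low severity, free to correct

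*SAP*

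**What the plan says.** SAP 2.2.1 lists "Vital signs including body weight" among the secondary safety endpoints. The analysis is in SAP 4.7.3: "Results of vital signs and body weight will be summarized by visit", followed by "Descriptive statistics for baseline and each treatment visit will be displayed". The section adds a subgroup for oral prophylaxis and by-subject listings with abnormal results flagged. It defines a baseline: Week 1 Day 1 for Naïve and Interrupted subjects and for Continuation subjects without end-of-study assessments from the preceding trial. For the others, "For “CSL830-Continuation” Subjects who complete the assessments at the CSL830_3001 End of Study Visit, these assessments will be the baseline". No change from that baseline is planned.

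SAP 4.7.2.3 handles hematology, biochemistry and coagulation with almost the same sentence but goes further: "Descriptive statistics for baseline and each treatment visit, including changes from baseline to each treatment visit". It also has a rule for gaps: "If the baseline value for a subject is missing, no change from baseline will be calculated for the subject".

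Two features of SAP 4.1 govern who is in each column. Treatment Period 1, Treatment Period 2 and the Extension are presented jointly. Safety columns follow the dose actually being taken, so that "a subject contributes events or assessments to each treatment received". On numbers, Protocol 3.5 has about 110 subjects randomized, 100 completing, and, for United States completers: "Approximately 50 of these subjects are anticipated to enroll in the Extension Period".

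**The concern.** A reader of the planned table will compare the baseline column with later visit columns and read the difference as change over time. That works only if the columns hold much the same people. Here the group roughly halves after Week 53, and not at random: the Extension takes United States subjects who completed Treatment Period 2 and chose to continue. A drift in mean blood pressure, pulse or weight could then appear although no subject changed, or a real drift could be masked. Enrollment from age 6 (Protocol 4.1.2) adds growth as a genuine within-subject weight change, which raw column means would mix with turnover.

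The dose columns raise a related question. A subject whose dose is increased moves to another column, and the SAP does not say which column or columns show that subject's baseline.

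**Working it through.** **Comparison of text.** The two SAP sections share the same by-visit layout and both define a baseline. Only 4.7.2.3 uses it for change scores and only 4.7.2.3 has a missing-baseline rule. SAP 4.14, which lists departures from the protocol, gives no reason for the difference. The descriptive statistics defined in SAP 4.1 (mean, SD, range, median, quartiles, counts of missing and non-missing) include no change score.

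**Inputs from the documents.** Randomized: about 110. Withdrawals: up to 10%. Completers: 100. Extension: about 50. Dose increases: assumed to be a minority, for example under 20% (SAP 4.14). The plan's own completer count reproduces: 110 × 0.90 = 99, or about 100. The plan gives no figure for vital signs, so any difference between groups of subjects, D below, is an assumption shown over a range.

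**Visit columns.** Set every subject's own change to zero. If the 50 Extension subjects differ by D from the other N − 50, the mean of all N lies D × 50/N above the others' mean, and the mean of the Extension subjects lies D above it. The pooled mean therefore moves by D × (1 − 50/N).

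- From Week 53 (N = 100): 1 − 50/100 = 0.50.
- From baseline (N = 110): 1 − 50/110 = 0.545.
- D = 2: 1.0 to 1.1 units.
- D = 5: 2.5 to 2.7 units.
- D = 10: 5.0 to 5.5 units.

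A within-subject change row would read zero in every case.

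**Dose columns.** Assume 55 subjects per arm. If a fraction f leaves the 40 IU/kg column and those leaving differ by D from those staying, that column moves by D × f. If 55f subjects enter the 60 IU/kg column at D from its mean, and moves to 80 IU/kg are ignored, it moves by D × 55f/(55 + 55f).

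- f = 5%, D = 2: 0.1 in either column.
- f = 20%, D = 10: 2.0 in the 40 IU/kg column; 10 × 11/66 = 1.7 in the 60 IU/kg column.

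The 20% is a ceiling: the SAP's figure is for all subjects over the whole study, with no rate per arm.

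**Whether the defined baseline exists.** SAP 4.7.3 places baseline at Week 1 Day 1 for Naïve and Interrupted subjects. The protocol's schedule of events for these subjects, and sections 8.4.2 and 8.4.3.1, put their vital signs at Screening and list none on Day 1. Protocol 3.2 records their baseline weight at Screening, although it also refers to a Day 1 weight. Unless Screening and Day 1 fall on the same day, which is allowed, a change score under the present definition would be missing for most of these subjects. Their number is not given.

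**The case against.** The strongest reply is that little depends on this table. No hypothesis or decision rests on it. Vital signs are a secondary endpoint only in the SAP: Protocol 2.2.2 does not list them, and Protocol 10.3 names them as an assessment. The table is not confined to means, and its counts will show the fall in numbers. Individual safeguards exist: abnormal values are flagged in listings, weight is compared with each subject's own baseline against a 10% limit (Protocol 3.2), a heart rate above 100 enters the pulmonary embolism score, and unfavorable signs can be reported as adverse events. Through Week 53 the pooled column holds largely the same 100 to 110 people. The table shells are a separate document and may show a change column.

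Most of this stands and sets the severity. It does not remove the point. Counts show how many left, not whether those remaining differ; flags catch values outside a limit, not a drift within limits; and the SAP text plans no change column.

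Some stronger readings are tempting but unsupported:

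- A reader might infer that an up-titrated subject's baseline stays in the starting-dose column. The SAP is silent on this.
- A reader might infer that the laboratory section already carries baseline across dose columns. It contains no such rule.
- A reader might treat the shift as United States versus elsewhere. The contrast is Extension versus non-Extension subjects: United States subjects who withdraw or decline are in the second group, and no regional split is given.

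**Conclusion.** The point holds as a low-severity improvement. The raw visit columns in SAP 4.7.3 do not estimate within-subject change, mainly once the Extension begins. The multiplier of 0.50 to 0.55 follows from the planned numbers; the size in mmHg or kg depends on an Extension versus non-Extension difference that the documents do not give, and it is zero if the groups are alike. Dose-column movement is secondary, and the pooled ≥ 40 IU/kg column is not affected by it. The documents do not support a claim that important individual changes would go undetected. Sample size, power and error rates are untouched.

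**What to change.** Amend SAP 4.7.3 in three places.

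1. Add summaries of change from baseline at each treatment visit for every vital sign and for weight, with the missing-baseline rule already used in 4.7.2.3.
2. State that after a dose increase a subject's change is still taken from that subject's own pre-treatment baseline and is shown in whichever dose column the visit falls in. This is a new rule and should also be written into 4.7.2.3.
3. For these tables, define baseline as the last value before the first CSL830 injection in this study, so that Screening values count for Naïve and Interrupted subjects and end-of-study values from CSL830_3001 continue to count for Continuation subjects. This concerns the summary tables only, not the weight used for dosing.

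The cost is a few sentences and extra rows or columns in tables already planned. The measurements are already scheduled.
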